### • Study design, including data sources

#### *Study Design*

A retrospective cohort study will be conducted using data from the PEDSnet database to achieve the study objectives. Electronic health record (EHR) data will be collected from January 2009 to December 2018. Two mutually exclusive cohorts will be identified, the first

cohort consisting of pediatric patients treated with higher than the recommended IV LCM doses, and the second (comparator) cohort comprising pediatric patients treated with recommended initial/maintenance IV LCM dose. The index date will be defined as the initiation of a new IV LCM treatment episode/receipt of a higher IV LCM dose than known maintenance dose. The exposure period will be the period between the index date (as defined above) and discontinuation of LCM. Subjects will be followed from the index date up to 30 days after discontinuing treatment with LCM or censoring, and during this time will be assessed for occurrence of described study outcomes. All subjects require a baseline period prior to the index date free of either oral or IV LCM. In the stratified assessment of increasing LCM loading dose, follow up will be from the index date up to 24 hours and 7 days after discontinuing treatment with IV LCM. Outcome ascertainment will be done in two ways, 1) data elements within the PEDSnet common data model (CDM) will be examined to identify select medical events of interest; and 2) a chart review of the EHRs for all eligible study patients will be conducted to examine unstructured, text data not captured in the CDM to identify the select medical events of interest.

Patients with status epilepticus diagnostic codes in their record will be identified from the cohort and will have their results presented separately in sub tables. They will also contribute to the main study populations. This is to fulfill commitment to examine outcomes in SE patients when exposed to lacosamide.

- **Data analysis**

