## 5 METHODOLOGY

### 5.1 Study design

This will be a retrospective cohort study that will use data from the PEDSnet database to estimate the incidence of select medical events for 8 SOCs and 3 SMQ terms and specific medical events included in these broad categories, and examine the effect of increasing IV LCM loading dose on the incidence of these select medical events. The study will also compare the incidence of the selected medical events in pediatric patient (aged  $\geq 1$  month  $< 17$  years) treated with higher IV LCM doses (including UCB's defined loading dose) to the incidence of these events in pediatric patients treated with a recommended initial/maintenance IV LCM dose.

The study will use electronic healthcare records (EHR) data from the PEDSnet data network, collected from the earliest (2009) through the latest date that data are available (~2018) for each included patient. The cohort design will allow the identification of pediatric patients treated with higher IV LCM doses or a recommended initial/maintenance IV LCM dose, and the ability to follow them to identify the occurrence of outcomes of interest.

[figure not shown]
The study will consist of two mutually exclusive cohorts. The first cohort will consist of pediatric patients treated with higher IV LCM doses (including UCB's defined loading dose).

The second, the comparator cohort will comprise of pediatric patients treated with recommended initial/maintenance IV LCM dose. The index date will be defined as the initiation of a new IV LCM treatment episode/receipt of a higher IV LCM dose than known maintenance dose (described in detail in Section 5.3.1). The exposure period will be defined as the time between the index date (as defined above) and discontinuation of IV LCM (described in more detail in Section 5.5.4). Demographic characteristics will be defined at the index date. Baseline data will be used to define clinical characteristics, LCM exposure indications and identify prevalent cases of the selected medical events of interest. Each subject will be followed from the index date up to 30 days after discontinuing treatment with IV LCM. During the follow-up period, data will be assessed for occurrence of the select medical events, defined in Section 5.5.5.

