### 5.2.1 Inclusion Criteria

- Patients with at least one iv LCM administration (earliest administration defines index date)
- At least 1 encounter with iv LCM administered between ages of  $\geq 1$  month and  $< 17$  years

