### 5.3.3 Follow-up (post-index) period

The duration of follow-up is for a maximum of 37 days from index date.

IV LCM treatment may span several days; treatment will be considered continuous if subsequent IV LCM treatment is noted to occur within 7 days of a previous treatment. If 7 days pass without a documented iv or LCM treatment, the index exposure has ended. Follow then continues until end of follow up or until the following censoring conditions apply:

Censoring: Patients will be followed for either 37 days OR until the patient is lost to follow-up[transfer out]; OR the patient is discharged from the in-patient setting [events that occur at home are not easy to track and are not included here; outpatient setting events are also excluded as we do not know what the patient has been doing at home during routine care]; OR the patient dies; OR the patient switches to another AED instead of/or adjunct to LCM; whichever comes first.

Clarification of follow up: The purpose of the study is to evaluate iv loading dose and higher subsequent dosing risk. Some patients may receive only one iv loading dose and then transfer to oral dosing which may last some weeks in the hospital setting. In the case where a patient has just one dose of iv LCM and switches to continuous oral LCM therapy, the follow up for AE evaluation will cease after a maximum of seven days of oral therapy or until censoring occurs as above. The same applies for those exposed to one dose of iv LCM and no further LCM exposure (either oral or iv).

Patients who have more than one dose of iv LCM and then switch to oral therapy will have a maximum follow up of 37 days of follow up index date or until censoring.

Patient time is contributed until either end of follow up or censor point (in days).

Patients are only included once in this study, so if we find evidence of a further iv loading dose of LCM given 6 months later say, they do not contribute to the study.

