**Table 2 NDC codes for Lacosamide**

NDC	Description
00131181067	lacosamide 10 mg/ml injectable solution [Vimpat]
001311810	lacosamide 10mg/ml intravenous injection [Vimpat]
68842081067	lacosamide 10 mg/ml injectable solution [Vimpat]
00091181067	lacosamide 10 mg/ml injectable solution [Vimpat]

The treatment episode for IV LCM will be defined based on the prescription/dispensing information including dosage, formulation, date and time (as available in the database).

The IV LCM loading dose will be defined, where possible, as the single, initial high IV LCM dose which is followed within approximately 12 hours by a subsequent lower maintenance dose.

As we are evaluating IV LCM, which is usually administered in a hospital (inpatient) setting, it is anticipated that in most cases detailed dosage information will be recorded in the patients' medical chart with detailed information on individual IV LCM doses administered, including exact dosage data and time stamps indicating time of administration. This will enable the capture of IV LCM loading dose and the identification of subsequent episodes of IV LCM loading dose exposure.

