### **5.9.1.2 Analysis of primary and secondary outcome measures**

Only the first occurrence of the event after the index date will be counted in analyses. For both the IV LCM group and comparator group, counts and frequency of events will be recorded. For both the IV LCM high dose group and comparator group, several incidence rates will be calculated. First, the overall incidence rate of any event of interest will be calculated. Second, incidence rates for each of the following events will be calculated individually: Cardiac disorders, Skin and subcutaneous tissue disorders, Nervous system disorders, Metabolism and nutrition disorders, Psychiatric disorders, Injury, poisoning and procedural complications, General disorders and administration site conditions, and Investigations, Drug reaction with eosinophilia and systemic symptoms syndrome, Severe cutaneous adverse reactions and Hypersensitivity events. Third, incidence rates for each subcategory of the abovementioned events and associated 95% confidence intervals will be calculated. The incidence rate of each event with associated 95% confidence interval will be calculated for the IV LCM high dose group and comparator group.

The numerator will be the total number of patients with the outcomes identified during the follow-up period. The denominator will be in patient-days. That is, the total summation of individual patient-days at risk up to the first occurrence of the AE of interest for subjects with

that AE, and the total patient-days at risk calculated up to the censoring date i.e. discontinuation of IV LCM plus 30 days or loss to follow-up for those subjects not experiencing that AE. Incidence rates will be presented with a 95% exact confidence interval based upon the Poisson distribution or another relevant model if there is nonconvergence. It is important to note incidence rates per time at risk are based on a constancy assumption. That is, the rates per unit of time assume that the event occurs with a constant rate over time. Events that are more likely to occur early or late relative to the initial exposure or with an increasing or decreasing hazard rate over time would not meet the constancy assumption and these rates should be viewed with caution. The person time for each patient will be calculated as the total number of days of follow-up as described in Section 5.3.3 .

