### 5.9.4 Strength and Limitations

**Unmeasured confounding:** As the study is comparing the incidence rates of select medical events in patients who are treated with a high dose of IV lacosamide to patients who are treated with recommended dose of IV lacosamide, the major confounders are factors that impact the incidence rate of these medical events of interest. These factors include age, gender, comorbidities, and exposure to other medications which are measured. Unmeasured confounding would only occur if there was a major confounder which is not measured and thus missed from the adjusted model. However, the electronic medical records include demographic information, the medical history of the patients and any medications prescribed by the physicians. Therefore we anticipate that information on most of the confounders will be available. It is possible that there will be missing information on some comorbidities, if they are not recorded by the physicians and on medications that are either bought over counter or prescribed outside the PEDSnet healthcare network. Nevertheless, most hospitals in the PEDSNet healthcare network are large with epilepsy comprehensive care centers within the neurology departments, so we anticipate reliable background medical. We do not anticipate that there will be a disproportionate difference in the recording of the medical history data and prescription of medications in patients who are treated with high dose lacosamide and recommended lacosamide prior to the index date. Therefore, we anticipate that there will be minimal unmeasured confounding. Additionally, the analysis will be using new user design to minimize confounding by indication.

**Reduced generalizability:** The PEDSnet database is restricted to subjects seeking and receiving medical care within a facility affiliated with PEDSnet. Data is obtained from multiple care sites and type (e.g. in-patient, out-patient, emergency department). However, if a report of an event was made or a subject was treated for an event at a facility that is not affiliated PEDSnet, this information will not be captured in the PEDSnet data. However, as most events are anticipated to occur within 24 hours of receiving IV LCM, the impact of this is likely to be low.

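### Section 5.9.1.2 counts events only after the index date, which as written leaves out the day of the first IV dose, although follow-up starts that day and most events are expected within 24 hours

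*Protocol*

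**What the plan says.** The index date is the day of the first IV dose (section 5.2.1): "Patients with at least one iv LCM administration (earliest administration defines index date".

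The counting rule is in section 5.9.1.2: "Only the first occurrence of the event after the index date will be counted in analyses".

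The follow-up statements begin on the index date itself. The study design summary has "Subjects will be followed from the index date up to 30 days after discontinuing treatment with LCM or censoring", and section 5.1 has "Each subject will be followed from the index date up to 30 days after discontinuing treatment with IV LCM". Section 5.3.3 sets the length: "The duration of follow-up is for a maximum of 37 days from index date". It also gives the unit: "Patient time is contributed until either end of follow up or censor point (in days". Section 5.9.1.2 likewise uses patient-days up to the first event. No section says how much time the index day carries.

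On timing, section 5.9.4 argues that events treated outside the network matter little, "as most events are anticipated to occur within 24 hours of receiving IV LCM". Section 5.5.4 (text under Table 2) expects charts to hold detailed dose records in most cases, "including exact dosage data and time stamps indicating time of administration".

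**The concern.** A programmer who applies section 5.9.1.2 as written selects events dated later than the index date. One who follows the summary, section 5.1 or section 5.3.3 starts on the index date. The protocol supports both and they give different numerators.

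Under the literal rule, the index day belongs to no window for most children: section 5.3.2 takes baseline conditions from data before the index date, and outcomes would start the day after it. Yet section 5.9.4 expects most events within 24 hours, and its misclassification paragraph relies on good recording of immediate events such as injection-site pain. Section 5.9.1.3 has no separate 24-hour analysis to recover them. The summary still mentions a 24-hour window, but counts it from discontinuation of IV lacosamide.

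Estimating incidence is the primary objective, so a rule that can remove early events matters even where the ratio between groups survives.

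**Working it through.** The protocol gives no event rate, group size or power calculation, so there is no figure to reproduce. The 875 in section 5.9.3 is a feasibility count. All other inputs below are assumptions.

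**1. Share of early events that fall on the index date.** Take dose times spread evenly over the day.
- Delays uniform over 24 h: share = 1/2 = 50%.
- Exponential delays with mean m days: share = 1 − m(1 − e^(−1/m)). Means of 12, 8 and 4 h (m = 1/2, 1/3, 1/6) give 57%, 68% and 83%.

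An event within 24 hours can therefore fall on the next date, where the literal rule keeps it.

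**2. Effect of leaving out index-day events.** Assume n = 875/2 = 437.5 per group, risk 20% (high dose) and 10% (recommended dose), children without the event followed 7 days, and later events at day 3. Let e be the events in a group and f the index-day share.
- Index-day events left out: rate = e(1 − f) / [3e(1 − f) + 7(n − e + ef)].
- All events counted, index day worth 0.5 day: rate = e / [0.5ef + 3e(1 − f) + 7(n − e)].

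High dose (e = 87.5) at f = 50%:
- left out: 43.75 / (131.25 + 2756.25) = 43.75 / 2887.5 = 15.2 per 1000 patient-days;
- counted: 87.5 / (21.875 + 131.25 + 2450) = 87.5 / 2603.1 = 33.6 per 1000.

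| Index-day share, high / recommended | High-dose rate, left out | Recommended-dose rate, left out | Ratio, left out | Ratio, all counted |
|---|---|---|---|---|
| 50% / 50% | 15.2 | 7.4 | 2.06 | 2.18 |
| 70% / 70% | 8.9 | 4.4 | 2.04 | 2.20 |
| 90% / 90% | 2.9 | 1.4 | 2.01 | 2.22 |
| 75% / 50% | 7.4 | 7.4 | 1.00 | 2.22 |
| 90% / 60% | 2.9 | 5.8 | 0.49 | 2.24 |
| 50% / 75% | 15.2 | 3.6 | 4.18 | 2.16 |

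The last row reverses the fourth to show the other direction. For the recommended group (e = 43.75), left out: 10.94 / (32.81 + 7 × 426.56) = 10.94 / 3018.75 = 3.62 per 1000, and 15.15 / 3.62 = 4.18. Counted: 43.75 / (16.41 + 32.81 + 2756.25) = 15.59 per 1000, and 33.61 / 15.59 = 2.16.

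With equal shares, 50% to 90% of events disappear and the ratio changes little. With unequal shares the ratio can move either way.

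**3. Person-time on the index day.** If index-day events are counted with zero days, pooled rates can still be formed and keep every event (ratios 2.19 to 2.27 in the first five scenarios). An individual-level Poisson fit with a log person-time offset fails on a zero-day row; with 0.5 day in its place it runs. If zero-day rows are dropped instead, the same events are lost (ratio 1.12 for 75% / 50%, 0.57 for 90% / 60%).

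**The case against.** The strongest reply is that no section says index-day events are excluded. Section 5.3.1 ties the index date to the start of a treatment episode and section 5.3.2 speaks of an index event, so the phrase in 5.9.1.2 may mean after the index dose. The superseded table in section 15, Item 3 used similar wording for a 24-hour window, which suggests the authors saw no exclusion in it. This stands as evidence of intent. It does not remove the conflict, because the current rule names a date and not a dose.

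Three stronger readings are tempting, and the documents do not support them.
- *The acute events are certain to be lost.* That follows only from the literal rule. Events on the next calendar date are kept in any case.
- *Index-day events carry zero days and fall out of the Poisson model.* The protocol gives days as a unit, without a rounding rule, and does not write out an offset. Fractional days fit the time stamps that section 5.5.4 expects. How a same-day event is timed is commonly settled in the statistical analysis plan, which is not shown, so its absence here is not an error.
- *The rate ratio is pulled towards 1.* An example does this: acute risks of 6% and 2% plus 4% later risk in both groups give 10/6 = 1.67, and losing 50%, 70% or 83% of acute events gives 7/5 = 1.40, 5.8/4.6 = 1.26 or 5.02/4.34 = 1.16. But those risks are assumed, they are risk ratios and not rate ratios, and equal later risk is doubtful because section 5.1 expects loading-dose children to be more often in refractory status epilepticus.

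It is also fair to object that counting every index-date event has its own bias. Somnolence, loss of consciousness or arrhythmia may precede the dose on the day a child presents. The change below has to deal with that.

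**Conclusion.** The point holds as a conflict between a stated counting rule and the stated start of follow-up. Section 5.9.1.2, taken as written, omits the dosing day; the summary and sections 5.1 and 5.3.3 start on it; section 5.9.4 puts most events close to it.

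If the literal rule is applied, incidence rates are understated by roughly the share of events that fall on the index date. That share is not known from the protocol; 50% to 90% was assumed here. Distortion of the rate ratio is conditional on the share differing between dose groups, and neither its size nor its direction can be fixed from the documents. The conflict is worth resolving before the analysis is run, because it affects the primary estimates and is cheap to correct.

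**What to change.** In section 5.9.1.2:
- Count the first event occurring after the first IV lacosamide dose, including events later on the index date, using dose and event time stamps where both exist.
- Give the index day non-zero person-time for all children, including those with an event that day and those censored that day by discharge or by another antiepileptic drug under section 5.3.3.
- Report results both with and without index-date events that have no recorded time.

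Align the follow-up wording in the summary and in sections 5.1 and 5.3.3 with this.

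The cost is a few sentences, a small programming change and one extra version of the results. The downside is possible misclassification of untimed index-day events, some of which may precede the dose; the two versions show how much depends on them.

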## 5.4 Study procedures

The medical chart reviews will only include patients who fulfill the eligibility criteria and are identified using the PEDSnet CDM data. Experienced healthcare personnel (e.g. neurologist or nurse) at each site will conduct any chart reviews.

Prior to study start, the CRF content (for use with extracted medical information) will be agreed by vendor and UCB.

#### 5.4.1 Plan for data collection

The PEDSnet database consists of electronic medical records and is not an administrative claims database. It consists of both structured and unstructured data that is recorded by physicians during all health encounters that patients have in the healthcare network.

The study primary outcomes will be ascertained in two steps; i) review of coded events in the common data model (CDM) and ii) medical chart extraction which will include both coded data and free text. PEDSnet uses Systematized Nomenclature of Medicine-Clinical Terms (SNOMED-CT) to represent the diagnoses; SNOMED-CT, ICD-9, ICD-10, CPT-4 and HCPCS codes to map procedures; RxNorm for dispensed and prescribed medications; and LOINC to represent laboratory results observations. The medical charts are considered the gold standard as they contain the original source of information for the medical encounters and include free hand information that is recorded by the physician during a health encounter. Therefore, including the medical chart review in addition to using data from the CDM will ensure that all available clinical information is utilized to validate the database findings and answer any queries.

**First step:** The PEDSnet network uses SNOMED-CT to enable standardization and pooling of diagnoses data across the across the 8 health systems included in the network. Initially, data will be evaluated relating to the study outcomes using the SNOMED-CT codes in the common dataset. The data in the CDM are coded using SNOMED-CT, an international logic-based, controlled vocabulary used in clinical care that enables meaning-based retrieval of clinical information from electronic health records. SNOMED CT is the most comprehensive, multilingual clinical terminology in the world, containing more than 300,000 medical concepts (diagnoses or findings), divided into hierarchies as diverse as body structure, clinical findings, geographic location and pharmaceutical/biological product. Each concept is represented by an individual code number and several concepts can be used simultaneously to describe a complex condition, for example presenting symptoms arising from a disease. This allows for separation of symptoms of drug exposure versus a comorbid chronic condition e.g. cardiac arrhythmia. Consequently, it is expected that the data in the CDM will include detailed information on the study outcomes.

**Second step:** Medical charts include the physician notes, laboratory results, EEG recordings and any other original and detailed information that will be used to evaluate or validate the study outcomes. To improve the validity of medical chart review results, at each site these chart reviews will be conducted by experienced healthcare personnel (e.g. nurse clinician) who will be given standardized training before starting the review and a manual of procedures and code set index for assistance. In the case of any queries, an experienced neurologist will be consulted.

The quality control process used to set up the common dataset is described in section 5.7.

The hierarchical level of final reporting of the adverse event outcomes will be agreed with the UCB safety physicians attached to each UCB product, but initially will be reported to include all events. Those not listed (as being specific to LCM) will be included under Section 5.5.1.1 – other diagnoses. In this way all events are captured.

A selection of patients (approximately 10%) will have their charts reviewed (proportion to be agreed post evaluation of final patient numbers and quality of data). As these are retrospective deidentified data, no patient or family consent is required. UCB will not be party to any personal information regarding patients such as name, address or any other identifying variable. Only pertinent medical and treatment data will be collected.

The medical chart reviewers will not be blinded to IV LCM dosage contained within the patient notes as they need to assess dose so that patients can ultimately be categorised into treatment groups at the time of analysis. However, to avoid observation bias, they will be blinded to the full study protocol including title, objectives, and to how study group assignment criteria are applied. Instead, they will be provided instructions as to how to perform data extraction and provided with a case report form to complete. It is assumed based on clinical practice that the information in the medical charts will only indicate the dosage that was prescribed to the patients and will not include language relating to “loading dose/higher dose or recommended dose” per se. Therefore, blinding the medical chart reviewers to the full protocol, will minimize the risk for ascertainment bias.

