Outcome ascertainment will be performed in two ways. First, data elements within the PEDSnet common data model (CDM), which comprises structured data extracted from EHRs will be examined to identify the select medical events of interest. Each event will be defined using algorithms that will include diagnostic codes and if needed procedure and medication codes, recorded in the EHR. Second, because not all symptoms, signs, and health problems are included in the structured data as diagnosis codes, a chart review of the EHRs for all eligible study patients will be conducted to examine unstructured text data not captured in the CDM to identify additional patients with the select medical events of interest.

Patients with status epilepticus diagnostic codes in their record will be identified from the cohort and will have their results presented separately in sub tables. They will also contribute to the main study populations. This is to fulfill commitment to examine outcomes in SE patients when exposed to lacosamide. It is assumed that any patients treated with a loading dose of LCM will be more likely to be in SE and proving refractory to treatment than the usual seizure presentation in children.

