### **5.7.2 Data Validity**

The study will use both the PEDSnet CDM and EHR medical charts data. The validity of the data depends on the source data that was recorded by the physician during each specific encounter. As indicated in the Section 5.7.1, PEDSnet has put in place extensive measures to ensure high validity of the data that is transferred into the CDM. For the chart review, a random sample consisting of 10% of all the EHR medical charts included in the study will be reviewed by a second reviewer and assessed for inter-person variability.

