**Misclassification:** Ascertainment of outcomes will be made using controlled vocabularies. Currently there are no validated algorithms for defining these outcomes in EHR data therefore there is a risk for misclassification. Misclassification will be minimized through chart reviews that will be conducted by experienced healthcare personnel. Additionally, sensitivity analyses will be conducted to assess the impact of the case definitions on the effect estimates. Information available from outpatient or ER reports is likely not to provide as complete information as that recorded during hospitalisation, however, despite this it is likely that any severe AEs will be recorded. As noted, available data from the chart review is expected to be

complete for patients in an inpatient setting. In particular nurses notes should comprise detailed information on patient responses and patient reported outcomes. As IV LCM is generally administered in an inpatient setting, we therefore expect recording of immediate AEs to be well documented, including those that may be less severe such as injection site irritation/pain.

**Strengths:** Despite these limitations, this assessment will provide a large sample pediatric of patients exposed to off-label IV LCM, facilitating timely characterization of the safety profile of these patients and informing the pediatric trial program.

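### The protocol fixes two incompatible extents of chart review for the primary outcomes, all eligible patients and about 10%, and does not say whether chart-found events count

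*Protocol*

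**What the plan says.** On extent, the study design part of the executive summary states that "a chart review of the EHRs for all eligible study patients will be conducted to examine unstructured, text data not captured in the CDM". Section 5.1 repeats this ("a chart review of the EHRs for all eligible study patients will be conducted") and explains that not every sign or symptom is coded, so the review serves "to identify additional patients with the select medical events of interest". Section 5.4.1, under its second step, says "A selection of patients (approximately 10%) will have their charts reviewed", with the "proportion to be agreed post evaluation of final patient numbers and quality of data". It does not say that the selection is random or balanced by dose group.

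On purpose, section 5.4.1 makes chart extraction the second of two steps for ascertaining the primary outcomes. It also describes the charts as a means of validating the database findings. The quality assurance text in section 5.7.1 mentions record review both for testing an algorithm on a sample and for study-specific data capture, without choosing between them.

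On use, section 5.9.1.2 defines a single numerator, the patients in whom an outcome was found during follow-up, with no separation by source. Section 5.9.4 relies on the review without giving a share: "Misclassification will be minimized through chart reviews that will be conducted by experienced healthcare personnel".

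Section 5.7.2 contains another 10%: "a random sample consisting of 10% of all the EHR medical charts included in the study will be reviewed by a second reviewer". This is a second reading to assess variability between reviewers.

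**The concern.** The primary objective is to estimate incidence, and section 5.5.5 concedes that no validated code algorithm exists for these outcomes. The extent of chart review therefore decides which events can be seen at all. Two teams working faithfully from this protocol could report different primary rates from the same children, one with all charts read and the other with about a tenth.

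The events most exposed are mild, early ones such as injection site pain. For these, section 5.9.4 itself looks to detailed nursing notes. If most notes go unread, the protection claimed there is missing for most patients.

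**Working it through.** The protocol gives no derived figure to reproduce here; 875 is a database count. The check has two parts.

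**1. Can the passages be reconciled?**
- The executive summary and section 5.1 give 100%; section 5.4.1 gives about 10%. All describe the first review of charts for outcomes.
- The 10% in section 5.7.2 is a second reading of charts already in the study, so it does not explain the 10% in section 5.4.1.
- Sections 5.3 and 5.4 restrict chart review to eligible patients. This fits either extent and settles nothing.
- Section 15 (amendments) does not mention the extent of chart review, so neither statement is superseded.

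**2. What follows from the 10% text?**

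Inputs:
- N = 875, the feasibility count in section 5.9.3 before the full criteria are applied.
- f = 0.10, the share reviewed (section 5.4.1).
- s = sensitivity of the codes. The documents do not give it; 0.3, 0.5 and 0.7 are assumed.
- Further assumptions: the reviewed share is representative, chart review finds every event, and codes are perfectly specific.

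Charts read = f × N = 0.10 × 875 = 87.5, about 88, leaving 875 − 88 = 787 children assessed by codes only. If the full criteria left 600 or 300 patients (illustrative), 60 or 30 charts would be read.

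If chart-found events count, capture = s + f(1 − s):
- s = 0.3: 0.3 + 0.1 × 0.7 = 0.37
- s = 0.5: 0.5 + 0.1 × 0.5 = 0.55
- s = 0.7: 0.7 + 0.1 × 0.3 = 0.73

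The counts fall short by 63%, 45% and 27%. The share of uncoded events left out is 1 − f = 0.90, whatever s is.

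If chart-found events do not count, capture = s (0.30, 0.50, 0.70) and every uncoded event is left out.

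If all charts are reviewed and count, f = 1 and capture is 100% under the same assumptions.

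Rate ratio under no true difference, with H the high-dose and R the recommended-dose group: [s_H + f_H(1 − s_H)] / [s_R + f_R(1 − s_R)]. With equal f and equal s this is 1.00.

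Second readings under section 5.7.2: 10% of 875 is about 88 if all charts are reviewed, and 10% of 87.5 is about 9 if only a tenth are.

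**The case against.** The strongest reply is that the harm is conditional. If the executive summary and section 5.1 govern, every chart is read and no event is missed for want of review. If section 5.4.1 governs and the sample is for validation only, as part of its wording allows, the numerator is not mixed. Sampling details and the handling of event sources may also sit in a statistical analysis plan that is not shown.

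Much of this stands. A reader might infer that the plan will mix two levels of ascertainment in one count. That requires both the 10% text and a decision to count chart-found events, and the protocol fixes neither. What the reply does not remove is the contradiction: an analysis plan cannot follow both extents, and validation-only use loses all uncoded events and gives up the case-finding purpose in section 5.1.

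Three other stronger readings are not supported:
- **A biased rate ratio.** Nothing in the protocol indicates that the review share or code sensitivity will differ by dose group, and section 5.4.1 keeps reviewers unaware of the objectives and the grouping criteria.
- **A share chosen after seeing outcomes.** The share depends on patient numbers and data quality, not on outcomes by dose group.
- **A rule that uncoded means absent.** Section 5.9.2 refers to what is missing from the electronic record, which includes free text (section 5.6.1). An event in an unread chart would in practice go uncounted, but section 5.9.2 does not prescribe this.

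**Conclusion.** The point holds as an internal contradiction about how the primary outcomes are ascertained; the protocol is wrong as written and must be corrected. The extent of review is stated as both all and about 10%, its purpose as both ascertainment and validation, and no rule says whether chart-found events enter the numerator.

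The size depends on the reading. With all charts read and counted there is no loss. On the 10% text, at least about 90% of uncoded events go uncounted, and the claim in section 5.9.4 fails for most patients. Capture is then at most 37%, 55% or 73% at assumed code sensitivity of 30%, 50% or 70%. These figures rest on complete chart review and perfectly specific codes; false-positive codes would offset some of the shortfall.

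The supported harm is to the absolute incidence rates. The rate ratio is affected only if the review share or code sensitivity differs by dose group. The missing statement on random or balanced selection leaves that possible but does not establish it.

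**What to change.** Reconcile the executive summary and sections 5.1, 5.4.1, 5.7.2 and 5.9.4 to one extent and one purpose of chart review. State that primary numerators use the same ascertainment source for every child. Then choose one of two rules.

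**(a) All charts.** Keep section 5.1, count chart-found events for everyone, and delete the 10% sentence in section 5.4.1. This needs up to about 787 more charts than section 5.4.1 implies, but no more than section 5.1 already promises.

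**(b) Coded events only.** Numerators use coded events from the common data model for all children. The sample of roughly 10% is fixed before outcomes are examined, drawn at random, stratified by dose group, and used only to describe overall sensitivity and positive predictive value of the codes. Correct the statements on full coverage, the case-finding purpose and the claim in section 5.9.4, and describe the rates as likely underestimates. The cost is wording and a sample draw; the price is a weaker claim of complete ascertainment.

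Under (b) the sample should not be asked to correct the rate ratio. At an assumed event risk of 5%, 88 charts hold about 88 × 0.05 = 4.4 true events, roughly two per group if the groups are equal in size, which is too few to estimate sensitivity by dose group.
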